2. OBJECTIVES

- 2.1. Primary Objective
 - > To develop a diagnostic prediction score for TB in hospitalized children with SAM

2.2. Secondary Objectives

- 1. To assess the prevalence of TB among hospitalized children with SAM
- 2. To describe the symptoms and clinical characteristics of TB disease in hospitalized children with SAM
- 3. To develop a first-step screening prediction score to identify children with presumptive TB among hospitalized children with SAM
- 4. To propose a stepwise diagnostic algorithm based on the score(s) developed
- 5. To assess the diagnostic performance and the added value in a diagnostic prediction score for TB in hospitalized children with SAM of the following tests:
 - a. Ultra performed on one NPA and one stool sample
 - b. Chest radiography features as assessed by the simplified TB-Speed CXR reading tool
 - c. Abdominal ultrasound
 - d. QuantiFERON®-TB Gold In-Tube (QFT) IGRA

- e. Monocyte-to-lymphocyte ratio (MLR)
- f. CRP
- 6. To assess the feasibility of collecting NPA and stool in children with SAM
- 7. To assess the safety and tolerability of NPA collection in children with SAM
- 8. To assess mortality and weight gain at 6 months in children with SAM, with or without anti-TB treatment
- 9. To assess the effect of bacteriological features (Xpert and/or culture-confirmed TB) and other key patient characteristics (age, HIV status, initial severity markers, percentage weight gain, CXR features) on TB treatment outcome
- 10. To evaluate the cost effectiveness of implementing the new diagnostic prediction score for TB treatment compared to the estimated effect of the standard of care in children with SAM.

3. STUDY ENDPOINTS

3.1. Endpoints for the primary objective

i) Sensitivity of the score obtained using predicted probability cut-off with the prediction model for the diagnosis of TB, defined as either confirmed or unconfirmed using the updated Clinical Case Definition for Classification of Intrathoracic Tuberculosis (see section 3.3)

ii) Specificity of the score obtained using predicted probability cut-off with the prediction model for the diagnosis of TB

- 3.2. Endpoints for the secondary objectives
 - 1. Proportion of confirmed and unconfirmed TB in the study population
 - 2. Clinical (symptoms, anthropometric measures, physical signs), laboratory (bacteriological, haematological, immunological signs) and radiological features (chest X-ray and abdominal US) of children with tuberculosis (confirmed and unconfirmed)
 - 3. Sensitivity and specificity of the score obtained using predicted probability cut-off with the screening prediction model for the identification of children with presumptive TB requiring further diagnostic evaluation
 - 4. Estimated time to TB treatment decision in hospitalized children with SAM, with and without presumptive TB based on the first-step screening prediction score
 - 5. Diagnostic accuracy measures (Sensitivity, specificity, negative and positive predictive value) of the different tests evaluated for the diagnosis of TB (Ultra performed on NPA and stools, CXR, abdominal ultrasound, QFT, MLR, CRP) and AUROC of diagnostic prediction models with and without the different tests results

Diagnostic accuracy of Ultra performed on NPA and stool samples will also be estimated against a specific microbiological reference standard including Ultra and mycobacterial culture from gastric aspirates (GAs)

- 6. Feasibility of NPA and stool specimen collection: proportion of children with samples collected as per study protocol
- 7. i) Safety of NPA collection procedure: adverse events (AEs) collected by study nurses (vomiting, nose bleeding, low oxygen saturation, respiratory distress)

ii) Tolerability of NPA collection procedure: discomfort/pain/distress assessed from the child (Wong-Baker face scale), by the parents (visual analog scale), by the nurses (FLACC behavioural scale) (quantitative assessment) measured in a subset of children

8. i) Mortality at 6 months, with or without TB treatment

ii) Percentage weight gain, WHZ at 6 months

- 9. TB treatment outcomes as defined per WHO recommendations [51]
- 10. Incremental cost-effectiveness ratio (ICER)

3.3. Reference diagnosis/case definition for the study and validation by the Expert Committee

Children will be classified into 3 categories, according to the updated Clinical Case Definitions for Classification of Intrathoracic Tuberculosis in Children [45], detailed in Table 2: *confirmed*, *unconfirmed*, or *unlikely* tuberculosis or any subsequent published update at the time of final case review if feasible and approved by the Scientific Advisory Board (SAB).

Case definition	Refined criteria
Confirmed tuberculosis	Bacteriological confirmation obtained (Mycobacterium tuberculosis confirmed by culture or Xpert MTB/RIF assay from at least 1 respiratory specimen)
	Bacteriological confirmation NOT obtained AND at least 2 of the following:
	 Symptoms/signs suggestive of tuberculosis¹
	CXR consistent with tuberculosis ²
Unconfirmed tuberculosis	• Close tuberculosis exposure or immunologic evidence of M. tuberculosis infection
	• Positive response to tuberculosis treatment (requires documented positive clinical response on tuberculosis treatment — no time duration specified)
	AND no spontaneous improvement of symptoms in the absence of antituberculosis treatment
Unlikely tuberculosis	Bacteriological confirmation NOT obtained AND criteria for "unconfirmed tuberculosis" NOT met (including spontaneous improvement of symptoms in the absence of antituberculosis treatment)

 Table 2. Updated Clinical Case Definition for Classification of Intrathoracic Tuberculosis

 in Children (adapted from Graham et al, 2015 [45])

¹ Clinical signs/symptoms suggestive of tuberculosis include: (a) Persistent cough: persistent (>2 wk), unremitting cough. (b) Weight loss/failure to thrive: (b1) Unexplained weight loss: >5% reduction in weight compared with the highest weight recorded in last 3 months OR (b2) Failure to thrive defined as (i) Clear deviation from a previous growth trajectory, and/or (ii) Documented crossing of percentile lines in the preceding 3 months, and/or (iii) Weight-for-age z score of ≤ -2 in the absence of information on previous/recent growth trajectory, and/or (iv) Weight-for-height z score of ≤ -2 in the absence of information on previous/recent growth trajectory AND (b3) Not responding to nutritional rehabilitation (or antiretroviral therapy if HIV infected). (c) Persistent unexplained fever: Persistent (>1 week) and unexplained fever (>38°C) reported by a guardian or objectively recorded at least once. (d) Persistent, unexplained lethargy or reduced playfulness: persistent, unexplained lethargy or decrease in playfulness/activity reported by the parent/caregiver. (e) Infants 0–60 day (or neonate): additional signs and symptoms suggestive of tuberculosis include: (e1) neonatal pneumonia or (e2) unexplained hepatosplenomegaly or (e3) sepsis-like illness.

² CXR will be considered consistent with tuberculosis if reviewers agree on the presence and location (right/left) of \geq 1 lesion among the following: alveolar opacity, bronchial compression, excavation, ghon focus, gibbus, miliary, nodular infiltrates, paratracheal nodes, peri-hilar nodes, pleural effusion, tracheal compression (as suggested by Graham et al. 2012 [52]).

CXRs will be read by 2 independent experts experienced in reviewing CXRs in children, blinded to all of the clinical information and to each other's interpretation. In case of disagreement, advice from a third expert will be sought.

An Expert Committee will be set up at national level for the purpose of case review and validation of TB diagnosis including causes of death in children who would die after inclusion in the study. The Expert Committee will not review all cases systematically. We will use an

algorithm to select children who will be reviewed. The Expert Committee will not review cases which are Ultra (bacteriologically)-confirmed TB cases, or true negative TB (Ultra-negative untreated children alive at 6 months with normal M6 follow-up CXR). The Expert Committee will review other cases considering the following parameters: initial and follow-up clinical data, microbiological data and radiological features.

The Expert Committee will classify children using the Revised Classification of Intrathoracic Tuberculosis Case Definitions for Diagnostic Evaluation Studies in Children (see Table 2 above), following Standard Operating Procedures (SOPs) specifically developed for the study. A centralized Expert Committee will review part of all cases reviewed at country level to ensure homogeneity of classification across countries.

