6. STUDY INTERVENTIONS

6.1. Description of the diagnostic strategy

The diagnostic strategy will include:

- Assessment of household TB contact history
- Medical history and duration of symptoms in the previous 4 weeks
- Physical examination including vital signs
- Clinical, anthropometric and biochemical assessment of malnutrition
- Clinical assessment for other non-dietary causes of malnutrition, including

identification of important comorbidities like HIV

- A digitalized CXR (standard anteroposterior and lateral view) performed and interpreted using standardised approach
- Ultra performed on NPA and stool samples, as well as on the first of the two GAs collected
- Mycobacterial culture performed on two GAs
- Abdominal ultrasonography to assess the presence of intra-abdominal lymphadenopathies or ascites
- MLR
- QFT
- CRP

TB diagnosis will be made according to national TB guidelines (i.e. clinician's diagnosis).

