8.2.2. Xpert MTB/RIF Ultra

The Ultra assay will be performed on the following samples:

- one untreated NPA (or sputum)
- one stool sample, with prior processing
- first GA out of two collected

Xpert testing will be done at the hospital laboratory on standard G4 platforms.

The Ultra assay will be carried out according to the manufacturers' guidelines and will be defined as positive, negative or invalid based on the manufacturers' recommended criteria.

Results will be interpreted as follows:

- In case of positive result for the presence of MTB (including "trace call" positive result) on any sample, the global result will be given as "MTB detected".
- In case of negativity of Ultra performed on the two samples, the global result will be given as "MTB not detected".
- In case of an invalid or error result for MTB detection, the test will be repeated if sample volumes allow for it.
- In case of rifampicin resistance detected on one or more sample, the result will be given as "MTB detected, rifampicin resistance detected". Otherwise the result will be given as "MTB detected, rifampicin resistance not detected (or indeterminate)". Children with

rifampicin resistance detected by Ultra will have culture and phenotypic DST performed on leftovers from NPA and stool (with additional samples taken if needed), and will be started on empirical MDR-TB treatment according to national guidelines.

Ultra results will be communicated by the laboratory to the nurse or clinician as soon as the result is available.

In case of TB treatment failure or poor treatment response, appropriate samples will be performed and resistance to TB drugs will be assessed using methods available on sites (phenotypic DST or line probe assays).

Leftovers of NPA, sputum, GA and stool samples will be kept at -80°C for future ancillary/substudies.

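### The true-negative exemption from expert review omits culture, which Table 2 counts as confirmation, and the protocol leaves Ultra-negative and stool-only Ultra-positive status unsettled

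*Protocol*

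**What the plan says.** Section 3.3 classifies children by Table 2. Confirmed TB there means "Mycobacterium tuberculosis confirmed by culture or Xpert MTB/RIF assay from at least 1 respiratory specimen". Unlikely TB requires that no bacteriological confirmation was obtained and that the criteria for unconfirmed TB are not met.

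The same section then exempts two groups from review by the Expert Committee:

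- The first: "The Expert Committee will not review cases which are Ultra (bacteriologically)-confirmed TB cases".
- The second: "true negative TB (Ultra-negative untreated children alive at 6 months with normal M6 follow-up CXR".

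All remaining children are reviewed. A central committee re-reads part of the files that the country committees have reviewed.

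Section 6.1 includes "Mycobacterial culture performed on two GAs" in the work-up, and Ultra on NPA, stool and the first GA. Section 8.2.2 lists the same three Ultra samples. It reports MTB as detected if Ultra is positive "on any sample, the global result will be given as" positive, trace calls included. The negative rule begins "In case of negativity of Ultra performed on the two samples".

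Confirmed plus unconfirmed TB is the outcome for model development (section 4.2) and the reference for the primary sensitivity and specificity (section 3.1). Accuracy of stool Ultra is part of secondary endpoint 5 (section 3.2), which adds a separate microbiological standard based on Ultra and culture of GAs.

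**The concern.** The exemptions decide which children receive their reference status without anyone reading the file. They should therefore agree with Table 2, and the terms they use should have one meaning. Three things stand in the way.

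1. The true-negative rule uses Ultra, treatment, vital status and the month 6 film, but not culture. Table 2 gives culture the same standing as Xpert.
2. The rule depends on a child being Ultra-negative, and section 8.2.2 defines a negative on two samples after listing three.
3. The confirmed exemption does not state a specimen type, while Table 2 asks for a respiratory one and stool is among the Ultra samples.

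At stake is the outcome variable of the primary model, and separately the meaning of the specificity reported for stool Ultra.

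**Working it through.** There is no plan figure to reproduce here. The check applies each rule to the same result pattern.

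| Result pattern | Sections 3.3 (exemption) and 8.2.2 | Table 2 |
|---|---|---|
| A. All Ultra negative, GA culture positive, untreated, alive, normal month 6 film | True negative, not reviewed | Confirmed (culture) |
| B. Stool Ultra positive only; NPA and GA Ultra and GA cultures negative | MTB detected under 8.2.2; exempt as confirmed if that result is what 3.3 means | Not confirmed; unconfirmed or unlikely on the clinical criteria |
| C. NPA and stool Ultra negative, GA Ultra positive | Detected by the any-sample rule; not detected by the two-sample rule if the two are NPA and stool | Confirmed (GA taken as respiratory) |
| D. NPA and stool Ultra negative, GA Ultra missing or invalid | Not detected, on two results | Depends on culture and the clinical criteria |

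**Pattern A** is a direct conflict inside section 3.3. It takes a GA to be a respiratory specimen, which the protocol does not spell out. The routine cultures are all on GAs, so Table 2's culture route would otherwise be nearly empty.

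**Pattern B** is an ambiguity. Section 3.3 does not cite 8.2.2, but 8.2.2 holds the only rule in the protocol for a child's overall Ultra status.

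**Patterns C and D** show the conflict of 8.2.2 with its own list and with section 6.1. Pattern D is foreseeable: GAs are scheduled at D3 (section 7.3, Table 4) and are not attempted in some very sick children (section 7.4).

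**Stool specificity under pattern B.** Specificity = TN / (TN + FP), where FP is the number of stool-positive children classed as not TB. If every stool-positive child is classed as TB, FP = 0 and specificity = TN / TN = 100%, whatever the assay's real performance. The GA-based standard of section 3.2 does not use stool, so FP can exceed zero there.

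**Effect of one child, as a scale only.** Section 4.3 assumes 15% prevalence in 720 children with 10% missing data.

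- TB cases analysed: 720 × 0.15 × 0.90 = 97.2, about 97. At 80% sensitivity, 0.80 × 97 = 77.6 are detected.
- Moving one child into the TB group at a fixed cut-off gives 77.6 / 98 = 79.2% if the score misses the child (−0.8 points), or 78.6 / 98 = 80.2% if it detects the child (+0.2 points).
- Children without TB analysed: 720 × 0.85 × 0.90 = 550.8, about 551. Removing one changes specificity by at most 1 / 550 = 0.18 points.

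Section 12.2.1 chooses the cut-off to reach at least 80% sensitivity. Part of any shift would therefore appear in the cut-off and in specificity instead of in sensitivity.

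**The case against.** **Choosing whose file is read is not classifying the child.** Sections 3.3 and 4.2 say that children are classified by Table 2, and nothing says an unreviewed child escapes it. This stands in part: Table 2 could still be applied to exempt children from the database. But section 3.3 itself attaches the true-negative label, and exempt children reach neither the country committee nor the central one. The homogeneity check in the Expert Committee section of chapter 14 covers event validation forms and relevant database information. The protocol does not say whether exempt children have such forms.

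**The parenthesis in the confirmed exemption points to bacteriological confirmation, which Table 2 defines.** Read that way, a culture-positive child belongs to the confirmed group and a stool-only positive goes to review. This is a fair reading. For stool it means the protocol is ambiguous, not shown to be wrong. For culture it does not help: the child in pattern A then fits both exempt groups, with opposite labels and no order of precedence.

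**Pattern A is nearly empty.** Results go to the attending clinicians (section 4.2), and a culture-positive child who is then treated no longer meets the untreated condition. This stands, and it limits the size.

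**A GA-positive child is caught by the any-sample rule.** That is the likely intention. What remains is a sample count that disagrees with the list above it, and a negative result that can be declared without the third sample.

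**The SOPs may settle it.** Section 3.3 refers to SOPs for how the committee classifies the children it reviews; who is exempt is fixed in the protocol text.

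**Conclusion.** The true-negative exemption conflicts with Table 2 because it omits culture. Separately, the meaning of Ultra-negative is inconsistent between the two-sample rule and the three samples listed in sections 6.1 and 8.2.2. The status of a stool-only positive is left open, with a built-in 100% specificity of stool Ultra against the Table 2 reference if the 8.2.2 result is used. The additional GA-based standard is not affected.

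The number of children concerned cannot be computed from the protocol and is probably small. Each could shift the reference diagnosis. The per-child figures above rest on the section 4.3 assumptions and are a scale, not an estimate.

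Three stronger conclusions are tempting and are not supported:

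- *That all three discrepancies contradict Table 2.* The two-against-three conflict does not; it touches Table 2 only through the word Ultra-negative.
- *That stool-only positives certainly bypass review.* That needs a link from 8.2.2 to 3.3 that the text does not make. Where such a child meets the criteria for unconfirmed TB, the pooled outcome is TB either way.
- *That a large share of the confirmed group is affected.* The confirmed rates of 0.7% and 1.7% cited in section 1 would give 720 × 0.007 = 5.0 and 720 × 0.017 = 12.2 confirmed children, so a few misrouted files might look serious. But no count of such files exists, the rates come from other cohorts tested with Xpert and culture whereas this study uses Ultra, and the primary outcome pools confirmed with unconfirmed TB.

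**What to change.** For reference classification only, with no change to patient care:

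1. In section 3.3, define a true negative as negative on all valid Ultra results and on all GA cultures, untreated, and alive at month 6 with a normal film.
2. Limit the confirmed exemption to a positive culture or Ultra on a respiratory specimen, as in Table 2, and name the specimens that count as respiratory.
3. Send stool-only positives, and any other child with discordant Ultra and culture results who does not meet that definition of confirmed, to the Expert Committee.
4. In section 8.2.2, replace the reference to two samples with all samples tested.

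The cost is wording in two sections and the committee SOP, and a few more files for a committee that already exists.

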4. STUDY DESIGN

4.1. Study type

TB-Speed SAM is a multicentric, prospective diagnostic cohort study conducted in two countries with high and very high TB incidence (Uganda, and Zambia). It aims at assessing several diagnostic tests that could result in the development of a score and algorithm for TB treatment decision in hospitalised children with SAM.

4.2. Methodology

This will be a prospective cohort study enrolling 720 children with SAM (see 4.3. Sample size).

The diagnostic strategy will include an initial clinical, radiographic and bacteriological evaluation of all enrolled children. For the purpose of the study, additional diagnostic methods will be added and evaluated including: abdominal ultrasonography, QFT IGRA, MLR, CRP as well as alternative sample collection methods (NPA, stools samples). MLR, CRP, QFT, and abdominal ultrasound findings will be made available to the clinicians. Although not currently recommended by the WHO and NTPs, these tests may contribute to patient care. Training on how to interpret tests results will be provided during the study preparation phase (see Chapter 6.2), together with specific SOPs. In particular, caution will be recommended to avoid using these tests to rule out TB.

Clinicians will make a diagnosis using national TB algorithms (referred to as "the clinician's diagnosis"). Results will be provided to the attending clinicians, i.e. not members of the study, who will make the final decision to initiate TB treatment according to current National Guidelines.

At the end of the study, children will be retrospectively classified as confirmed, unconfirmed, or unlikely TB, using the updated version of the Clinical Case Definition for Classification of Intrathoracic Tuberculosis [45] (Table 2). For model development, the reference diagnosis will be *confirmed* and *unconfirmed* TB.

Using logistic regression, we will develop a score for TB diagnosis, considering confirmed and unconfirmed TB as reference diagnosis, in hospitalized children with SAM. As a secondary objective, and in order to reduce costs, sample collection, and complexity of the diagnostic process, we will aim at developing a first-step screening score to identify children with presumptive TB who would benefit from further diagnostic testing. This will be done similarly using logistic regression with the individual predicted probability of TB dichotomized to maximise sensitivity as predicted variable. We will exclude the following tests from model development: Ultra results on microbiological samples, abdominal ultrasound, as well as CXR if possible. Both scores will be internally validated using resampling and will be incorporated in a stepwise algorithm to guide practical implementation of the screening and diagnosis process.

The stepwise algorithm will be discussed with local clinicians involved in the study to better adapt it for future use in their routine practice.

• Study design adaptation to the Covid-19 outbreak

All enrolments in the TB-Speed SAM study have been stopped as of April 1st, 2020 due to the Covid-19 outbreak. This was justified by the complete or partial lock down in project countries, the lack of protective equipment to ensure safety of participants and study staff, and the difficulty to conduct proper study monitoring. The decision was approved by the TB-Speed Scientific Advisory Board. All study sites were instructed: 1) to suspend all enrolments until further notice; 2) to conduct phone-based follow-up when physical visits are not possible, provided the participant's safety is not compromised, based on ad hoc Standard Operating Procedures for remote follow-up; 3) to limit face-to-face contact to that strictly necessary to provide care that cannot be suspended, provided the safety of staff is protected, based on ad hoc Standard Operating Procedures for infection prevention and control during health care, samples collection and samples processing at the laboratory.

Enrolments in the main TB-Speed SAM study will resume progressively at sites, on condition that the respective country situations allow for it, in particular the availability of personal protective equipment (PPE). The Covid-19 ancillary study will be implemented to document SARS-CoV-2 prevalence and its impact on outcome in children, and enable access to specific Covid-19 treatment if needed, as soon as approved by Ethics Review Committees.

